In each cohort, approximately 80 subjects will be enrolled to provide approximately 60 subjects in the Evaluable Set, defined as subjects who complete all planned treatments and most evaluations, including the Day 57 Follow-up visit. Therefore, a total of 160 subjects in 2 cohorts may be enrolled, but the sample size of Cohort 2 may be adjusted, depending on the results of Cohort 1.

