9.2 Discussion of Study Design, Including Choice of Control Groups

This is a nonrandomized, open-label study. No control group has been included.

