5.5.2 Local Skin Reactions

LSRs will be assessed using a 5-point grading scale ranging from 0 (Not Present) to 4 (Worst) for such signs as Erythema, Flaking/Scaling, Crusting, Swelling, Vesiculation/Pustulation, Erosion/Ulceration on the treatment area at the following visits: Day 1, Day 2, Day 3, Day 4 (Cohort 1 only), Day 5 (Cohort 1 only), Day 8, Day 15, Day 29, and Day 57. In addition, LSRs may be followed after the Day 57 visit to resolution, or if resolution is unlikely, to stabilization.

LSR baseline grades are defined as the LSR grades recorded at Day 1 (either pre-dose or post-dose).

The incidence of LSRs will be summarized by grade and cohort at each visit for each sign. In addition, LSR grades will be regarded as continuous values and will be summarized using descriptive statistics by cohort at each visit for each sign. Similarly, grades for each LSR sign will be visually presented in bar graphs by cohort at each visit.

Further, the incidence of the worst post-baseline LSR grade will be summarized by LSR grade and cohort for each sign.

The number of subjects with shift from baseline to the worst post-baseline grade and to the Day 57 grade will be summarized by cohort for each sign.

Furthermore, a composite LSR score will be constructed by summing the individual LSR grades for each sign at each visit. This composite score and change from baseline will be summarized by cohort at each visit using descriptive statistics. In addition, this score will be presented graphically by cohort in a line plot.

All LSR grades, including the derived composite score, and any associated comments will be displayed in data listings.

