9 PROGRAMMING SPECIFICATIONS

Analysis dataset specifications will be provided as a stand-alone document.

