11 MOCK TABLES, LISTINGS, AND GRAPHS

Mock tables, listings, and graphs will be provided as standalone documents.

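### SAP 5.5.2 takes the worst skin-reaction grade over 8 scheduled gradings in Cohort 1 and 6 in Cohort 2, and describes no summary on a common schedule

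*SAP*

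**What the plan says.** SAP 5.5.2 (Local Skin Reactions) grades six signs from 0 to 4. Its visit list marks two days as belonging to one cohort: "Day 4 (Cohort 1 only), Day 5 (Cohort 1 only), Day 8". The Day 1 grade is the baseline, so it is not a post-baseline grading in either cohort. Protocol 9.1.2 agrees that Cohort 2 subjects have no visit on Days 4 and 5. Protocol 9.5.1.5.8 has local skin reactions (LSRs) graded before application on dosing days.

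Two of the planned summaries use a maximum over visits. The first is the worst-grade table: "the incidence of the worst post-baseline LSR grade will be summarized by LSR grade and cohort for each sign". The second is the shift table: "The number of subjects with shift from baseline to the worst post-baseline grade and to the Day 57 grade will be summarized by cohort". Neither is restricted to particular visits, and no second version is described.

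The same section also plans by-visit grade tables, by-visit descriptive statistics and graphs, a composite score, and a listing of all LSR grades. Table shells lie outside the SAP: "Mock tables, listings, and graphs will be provided as standalone documents". So do the dataset specifications: "Analysis dataset specifications will be provided as a stand-alone document". Neither was available for this review.

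**The concern.** A maximum cannot fall when more observations are added. Cohort 2's scheduled days are a subset of Cohort 1's, so two cohorts with an identical reaction course could show different worst-grade distributions because of the schedule alone. The direction is known: the 3-day regimen would look milder.

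Day 4 shows this most clearly. If grading is done before application, as the protocol requires, both cohorts have had three applications by then, but only Cohort 1 is graded.

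SAP 5.1.2 lists LSRs within the secondary safety endpoint, and SAP 3.1.2 makes the contrast of 5-day with 3-day treatment on safety a secondary objective. What is at stake is a reader taking a scheduling artefact in these two tables for a difference between regimens.

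**Working it through.** **Count of gradings (SAP 5.5.2, with Day 1 removed as baseline).** The plan states no count, so there is no figure to reproduce.

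- Cohort 1: Days 2, 3, 4, 5, 8, 15, 29, 57 = 8.
- Cohort 2: Days 2, 3, 8, 15, 29, 57 = 6.
- Shared: Days 2, 3, 8, 15, 29, 57 = 6.

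These are scheduled counts. SAP 5.5.2 also allows follow-up of LSRs after Day 57 and does not say whether those grades enter the worst grade.

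**Direction.** For one subject, the maximum over 8 gradings is at least the maximum over the 6 shared ones. The proportion at grade g or worse therefore rises or stays the same for every g. A row for exactly grade g is a difference of two such proportions, so it can go either way.

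**Model for illustration.** All rates and correlations below are assumptions; none comes from the documents. Let p_j be the assumed probability of being at the grade or worse at visit j, c_j the matching normal cut-off, and ρ the within-subject correlation of an exchangeable Gaussian latent variable:

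P(grade or worse at any visit) = 1 − ∫ φ(u) ∏_j Φ((c_j − √ρ·u)/√(1−ρ)) du

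The product runs over all 8 visits or over the 6 shared visits. As a check at ρ = 0 with p = 0.10, this gives 1 − 0.9^8 = 57.0% and 1 − 0.9^6 = 46.9%.

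**Exact-grade rows.** Assume flat per-visit rates of 40% for grade 1 or worse and 20% for grade 2 or worse, with ρ = 0.5.

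- Over 6 visits: 77.7% and 52.2%, so exactly grade 1 is 77.68 − 52.24 = 25.4%.
- Over 8 visits: 81.8% and 57.6%, so exactly grade 1 is 81.84 − 57.58 = 24.3%.

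Both cumulative figures rise, while the exact grade 1 row falls.

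**How timing drives the size.** Assumed per-visit rates for Days 2, 3, 4, 5, 8, 15, 29, 57, with the same course in both cohorts:

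- (a) 10% at every visit.
- (b) 2, 8, 20, 10, 5, 1, 0, 0%: the peak is on Day 4, which makes this deliberately unfavourable.
- (c) 0.1, 0.5, 1, 3, 20, 5, 0, 0%: the peak is on Day 8, a shared day.

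The table gives the incidence of the grade or worse. The last column adds only Day 4 to the six shared days.

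| Course | ρ | 8 visits | 6 shared visits | Gap (points) | Gap from Day 4 alone |
|---|---|---|---|---|---|
| (a) | 0.5 | 36.7% | 32.1% | 4.6 | 2.5 |
| (a) | 0.7 | 28.8% | 25.8% | 3.0 | 1.6 |
| (a) | 0.9 | 19.5% | 18.2% | 1.3 | 0.7 |
| (b) | 0.5 | 29.4% | 12.6% | 16.8 | 13.3 |
| (b) | 0.7 | 25.4% | 11.0% | 14.4 | 12.1 |
| (b) | 0.9 | 21.3% | 9.1% | 12.2 | 11.5 |
| (c) | 0.5 | 23.3% | 22.2% | 1.1 | 0.2 |
| (c) | 0.7 | 21.5% | 21.1% | 0.4 | 0.1 |
| (c) | 0.9 | 20.1% | 20.1% | 0.02 | 0.0 |

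Gaps come from unrounded values. The full gap assumes that Cohort 2 would also have the assumed Day 5 rate. Before application on Day 5, Cohort 1 has had four applications and Cohort 2 three, so part of a real Day 5 excess could be a regimen effect. The last column avoids that problem, provided that Day 4 is graded before application.

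**The case against.** The strongest case on the other side is that nothing here is wrong. Each table correctly describes the worst grade observed in its own cohort, and the SAP shows the unequal visits in the same section. SAP 5.3 calls any contrast mainly noninferential, and the protocol says of the design: "This is a nonrandomized, open-label study. No control group has been included". All LSR grades are to be listed, so a common-visit worst grade can be derived from planned output, and the by-visit tables can be read at the shared days. The shells may already contain a footnote or a second version. A restricted table is imperfect too: it drops real on-treatment reactions in Cohort 1, and no table can recover Days 4 and 5 in Cohort 2.

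Much of this stands. It limits the harm to a misreading of descriptive tables, and it confines the point to the SAP text. It does not remove the point. A listing is not a summary, marginal by-visit percentages cannot be combined into a subject-level maximum, and showing the visit list does not tell a reader what it does to a maximum.

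A reader might also infer that every row for Cohort 1 is inflated. The documents do not support that: the artefact applies to a subject's maximum and to cumulative grade, and the exact grade 1 row above moved the other way.

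**Conclusion.** The point holds as a limited one. Following SAP 5.5.2 as written compares worst grade and shift to worst over 8 scheduled gradings against 6. For the same reaction course, the schedule alone can only raise the cumulative incidence in Cohort 1 relative to Cohort 2, or leave it unchanged. This rests on scheduled visits only. The equal-exposure reading of Day 4 also rests on grading before application; because the SAP accepts a Day 1 baseline graded before or after the dose, that timing cannot be taken as certain.

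The size cannot be determined from the documents. The assumed courses show that it depends mainly on when reactions peak: near zero if they peak on a shared day, and noticeable if they peak on Day 4. A reader might take the largest illustrated gap as an estimate or an upper limit. It is neither, because the rates are assumed, the figure is for cumulative grade, and it includes Day 5. Nor do the documents support the inference that the schedule could tip a choice between regimens, since no decision rule uses worst grade.

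**What to change.** Keep the all-visit tables. Add to SAP 5.5.2 a sentence such as: *Worst post-baseline grade and shift to worst grade will also be shown over the scheduled visits shared by both cohorts (Days 2, 3, 8, 15, 29 and 57), next to the all-visit version.*

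Footnote both versions with the 8 and 6 scheduled gradings. The footnote should also state two limits of the shared-visit version. It omits Cohort 1 reactions seen only on Days 4 and 5, and so may understate that cohort. Day 8 is nominally 8 − 5 = 3 days after the last application in Cohort 1 and 8 − 3 = 5 days after it in Cohort 2. For that reason neither version should be named as the governing one.

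The cost is one more run of existing table programs plus footnotes, with no new data and no change to visits. If the table shells already contain this, only the SAP sentence is needed.

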5.5.3 Pigmentation and Scarring

Presence or absence of pigmentation (including hypo-pigmentation and hyper-pigmentation) and scarring will be assessed on the treatment area at the following visits: Day 1, Day 2, Day 3

Day 4 (Cohort 1 only), Day 5 (Cohort 1 only), Day 8, Day 15, Day 29, and Day 57. In addition, pigmentation and scarring may be followed after the Day 57 visit to resolution, or if resolution is unlikely, to stabilization.

Results will be summarized by cohort at each visit. The number of subjects with shift from baseline to Day 57 will be summarized by cohort.

All pigmentation and scarring records with comments will be presented in data listings.

5.5.4 Laboratory Data – Hematology and Blood Chemistry

Laboratory assessments for hematology and blood chemistry will be performed at Screening, Day 8, and Day 57.

Actual values, changes from baseline, and percentage change from baseline for the following laboratory parameters will be summarized by cohort at each visit using descriptive statistics.

- Hematology:

Red Blood Cells, Hemoglobin, Hematocrit, Platelets, White Blood Cells, Neutrophils (Absolute Count), Neutrophils (%), Lymphocytes (Absolute Count), Lymphocytes (%), Monocytes (Absolute Count), Monocytes (%), Eosinophils (Absolute Count), Eosinophils (%), Basophils (Absolute Count), Basophils (%), Mean Corpuscular Volume, Mean Corpuscular Hemoglobin, Mean Corpuscular Hemoglobin Concentration, Red Blood Cell Distribution Width

- Blood Chemistry:

Electrolyte: Sodium, Potassium, Chloride, Carbon Dioxide

Liver Function: Alkaline Phosphatase, Aspartate Aminotransferase (AST), Alanine Aminotransferase (ALT), Gamma-glutamyl Transferase (GGT), Bilirubin (Total), Bilirubin (Direct)

Renal Function: Blood Urea/Blood Urea Nitrogen, Creatinine

Other: Glucose, Calcium, Albumin, Cholesterol, Triglycerides, Phosphorus, Lactate Dehydrogenase (LDH), Total Protein, Uric Acid

These laboratory parameters will also be analyzed using shift tables by post-baseline visit (Day 8 and Day 57) and cohort.

Listings of all hematology and blood chemistry values will be provided with abnormalities flagged.

5.5.5 Laboratory Data – Urinalysis

Urinalysis assessment will be performed at Screening, Day 8 and Day 57. All parameter values will be provided in a data listing with abnormalities flagged.

5.5.6 Vital Signs

Vital signs (systolic/diastolic blood pressures, pulse rate, respiratory rate and body temperature) will be assessed at the following visits: Screening, Day 3 (Cohort 2 only), Day 5 (Cohort 1 only), Day 8, Day 15, Day 29, and Day 57.

Actual values, change from baseline, and percentage change from baseline for each vital sign parameter will be summarized using descriptive statistics by cohort at each visit.

A listing of vital sign values will be provided with flags for those outside (above or below) the reference range (see Section 12.2).

5.5.7 12-Lead Electrocardiograms

A 12-lead ECG will be completed at Screening, Day 1 (4 hours postdose, Cohort 2 only), Day 3 (4 hours postdose, Cohort 2 only), Day 8, and Day 57 to assess rhythm, heart rate, and intervals (PR, QRS, QT, and QTcF).

QTc will be collected. Study sites may have applied different formulae for calculation of QTc, therefore, this parameter will be reported in a data listing, but will not be analyzed.

For heart rate and ECG intervals, actual values, changes from baseline, and percentage change from baseline will be summarized using descriptive statistics by cohort at each visit.

Additionally, a listing of subjects with clinically significant abnormal ECG results will be presented.

All 12-lead ECG data, including details of abnormal findings from investigators, will be provided in a subject listing.

5.5.8 Other Safety Analyses

Physical examination findings at Screening and Day 57 will be listed for each subject.

Weight will be measured at Screening and Day 57. Actual values, change from baseline, and percentage change from baseline will be summarized by cohort and visit.

Results of pregnancy tests will be listed for subjects if applicable.

6 ONGOING ANALYSES

A formal interim analysis is not planned. Since this is an open-label study, after each group of approximately 20 subjects, ongoing analyses will be performed with tabulation of activity, LSRs, and adverse events.

7 CHANGES IN THE PLANNED ANALYSES

Definition of the Evaluable Set is updated to include Day 1 and Day 57 AK lesion evaluations only.

The Recurrence Follow-up Set is defined in this document to analyze data collected during the Recurrence Follow-up Period.

AK recurrence is not listed as a discontinuation event on CRF. The Sponsor reviewed all collected disposition event details and recategorized the subjects who discontinued due to AK recurrence in the Recurrence Follow-up Period into a new category of primary reason for discontinuation - "AK recurrence" (See Section 12.3).

The recurrence rates and the sustained response rate will be estimated with a Kaplan-Meier method to consider censored subjects who discontinued due to non-AK recurrence reasons.

8 DEFINITIONS AND CONVENTIONS FOR DATA HANDLING

8.1 Baseline Values

Unless stated otherwise, baseline values are defined as the last non-missing data collected before or on the first dose date/time, which would be either, the Screening or Day 1 visit.

8.2 Adverse Event Relationship to Study Drug

If an adverse event relationship to study drug is missing, it will be considered as related to study drug.

9 PROGRAMMING SPECIFICATIONS

Analysis dataset specifications will be provided as a stand-alone document.

10 STATISTICAL SOFTWARE

Statistical software SAS[®] v9.4 will be used for all summaries and statistical analyses.

11 MOCK TABLES, LISTINGS, AND GRAPHS

Mock tables, listings, and graphs will be provided as standalone documents.

